### Rescue medication use within 24 hours post dose

- Rescue medication use within 24 hours post dose is defined as: first rescue medication date/time – intervention date/time (in hours)  $\leq$  24 hours. Participants with first rescue medication date  $\leq$  intervention date +1 day and missing first rescue medication time are excluded.

### PGIC overall status improvement over Time

At time point X, participants who meet both of the following criteria are classified as responders (PGIC overall status improvement):

- PGIC overall status improved (defined as very much improved, much improved, or minimally improved) at X, i.e., in the X analysis window
- No rescue medication taken at or before the PGIC assessment in the X analysis window.

At time point X, participants who are not responders are classified as failures. Failure criteria include any of the following:

- Rescue medication taken at or before X (RM=F)
- PGIC overall status not improved (defined as no change, minimally worse, much worse, or very much worse at X)
- Missing PGIC overall status at X (NC=F).

### Appendix 2.1.2. Rescue Medication = Failure (RM=F) Algorithm

Efficacy assessments that are affected by the RM=F algorithm are pain intensity, nausea status, photophobia status, phonophobia status, and functional disability level.

Let X denote a postdose time point: 15, 30, 45, 60, or 90 minutes; 2, 3, 4, 6, 8, 24, or 48 hours.

If study intervention start date/time is from the eDiary Migraine Report, then it can be linked with its corresponding data at postdose time point X.

For a given assessment at time point X, the objective is to determine whether any rescue medication is taken at or before that assessment, even if the assessment is missing.

Rescue medication taken at or before time point X (RM=F) is defined as either (1) or (2):

- 1) Rescue medication taken at or before the assessment in the X analysis window. Defined as either of the following if the assessment is non-missing in the X analysis window:
  - (first rescue medication date/time  $\leq$  {eDiary finding date/time for the assessment in the X analysis window}, if first rescue medication time is not missing

- (first rescue medication date  $\leq$  {eDiary finding date for the assessment in the X analysis window}, if first rescue medication date is not missing but time is missing
- 2) Rescue medication taken at or before the missing assessment in the X analysis window. Defined as either of the following if the assessment is missing in the X analysis window:
  - (first rescue medication date/time – study intervention start date/time)  $\leq$  upper bound of the X analysis window (see [Table 2](#)), if first rescue medication time is not missing
  - first rescue medication date  $\leq$  study intervention start date + Y days, if first rescue medication date is not missing but time is missing
    - If X < 24 hours, then Y = 0.
    - If X = 24 hours, then Y = 1.
    - If X = 48 hours, then Y = 2.

090177e1a3a7d3d9\Approved\Approved On: 30-May-2025 05:10 (GMT)

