### **6.9.2. Rescue Medication**

The study site will not supply rescue medication that will be obtained locally by participants. The date and time of rescue medication administration as well as the name and dosage regimen of the rescue medication must be recorded.

In all circumstances, the participant will always continue to complete the handheld entries through the 48-hour assessment after taking the study intervention. A Rescue Medication paper diary will be provided to participants at the Baseline Visit. Participants will record any rescue medication taken on the Rescue Medication paper diary and return to the site at the EOT Visit.

After administration of study intervention, **ALL other headache medication** is prohibited during the first 2 hours postdose of study intervention administration. A participant who does not experience relief of their migraine headache at the end of 2 hours after administration of study intervention (***and after the 2-hour assessments have been completed on the handheld device***), will be permitted to use ONLY the following rescue medication: ***aspirin, ibuprofen, acetaminophen up to 1000 mg/day (this includes Excedrin Migraine), naproxen (or any other type of NSAID), antiemetics (ie, metoclopramide or promethazine), or baclofen. These are the only medications allowed for rescue treatment after 2 hours postdose of study intervention.***

If the migraine is relieved by study intervention at 2 hours postdose but then returns to a moderate or severe pain intensity level between 2 and 48 hours postdose, the participant will be permitted to take the same rescue therapy as outlined above.

During the 45 days of the Treatment Phase, if the participant has a nonqualifying migraine (attack with mild pain) or a migraine that they do not treat with study intervention, the participant is permitted to use only the following medications: ***aspirin, ibuprofen, naproxen (or any other type of NSAID), antiemetics (ie, metoclopramide or promethazine), or baclofen.***

After completing all assessments in their handheld (through 48 hours postdose and before returning to the clinical site for EOT Visit), if participants experience a migraine, they are allowed to take their prescribed standard of care medication per local practice (including triptans if not contraindicated and acetaminophen up to 1000 mg/day, this includes Excedrin Migraine or other similar combination products), provided the medication is not otherwise prohibited.

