### 2.2. Study Objectives, Endpoints, and Estimands

Type	Objective	Endpoint	Estimand
	Primary:	Primary:	Primary:
Efficacy	
 
• To compare the efficacy of zavegepant with placebo in the acute treatment of migraine.
 
	
The following co-primary endpoints will be tested:
 
 
• Percentage of participants with a pain intensity of none (pain freedom) at 2 hours postdose.
 
	
Co-primary estimands:
 
 
• The estimand is the treatment effect of zavegepant relative to placebo in terms of the difference in percentage of participants with a pain intensity of none at 2 hours postdose among all randomized participants with migraine headache of moderate or severe intensity who took study intervention. Intercurrent event of taking rescue medication at or
 

Type	Objective	Endpoint	Estimand
		
 
Percentage of participants with an MBS reported before dosing that is absent at 2 hours postdose.
 
	
before 2 hours postdose will be regarded as a failure.
 
 
The estimand is the treatment effect of zavegepant relative to placebo in terms of the difference in percentage of participants with an MBS reported before dosing that is absent at 2 hours postdose among all randomized participants with migraine headache of moderate or severe intensity who took study intervention. Intercurrent event of taking rescue medication at or before 2 hours postdose will be regarded as a failure.
 

	Secondary:	Secondary:	Secondary:
	Key Secondary:	Key Secondary:	Key Secondary:
Efficacy	
 
To compare zavegepant with placebo for measures of early pain relief.
 
	
 
Percentage of participants with a pain intensity of none or mild at 15 minutes postdose.
 
	
 
The estimand is the treatment effect of zavegepant relative to placebo in terms of the difference in percentage of participants with a pain intensity of none or mild at 15 minutes postdose among all randomized participants with migraine headache of moderate or severe intensity who took study intervention. Intercurrent event of taking rescue medication at or before 15 minutes postdose will be regarded as a failure.
 

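### A rescue record with a date but no time fails the participant at every assessment on that calendar date, including 15 minutes to 2 hours, even when the rescue was permitted and taken later that day

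*SAP*

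**What the plan says.** SAP Appendix 2.1.2 defines the rescue-equals-failure rule (RM=F). Its stated aim is a matter of order in time: "the objective is to determine whether any rescue medication is taken at or before that assessment, even if the assessment is missing". It covers all twelve time points: "Let X denote a postdose time point: 15, 30, 45, 60, or 90 minutes; 2, 3, 4, 6, 8, 24, or 48 hours".

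With a rescue time on record, the clock times are compared. Without one, only dates are compared:

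- Assessment present: failure if the first rescue date is on or before the "eDiary finding date for the assessment in the X analysis window}, if first rescue medication date is not missing but time is missing".
- Assessment missing: failure if the first rescue date is on or before the "study intervention start date + Y days, if first rescue medication date is not missing but time is missing", with the condition "If X < 24 hours, then Y = 0".

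Neither branch has a floor at 2 hours.

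The estimands are narrower. For the first key secondary endpoint, SAP Section 2.2 says: "Intercurrent event of taking rescue medication at or before 15 minutes postdose will be regarded as a failure". Protocol Section 6.9.2 says that all other headache medication is "prohibited during the first 2 hours postdose of study intervention administration", and it allows the listed rescue only after the 2-hour handheld entries. The same section requires the date and time of rescue to be recorded. The record is a paper diary (Protocol Section 8.2.3).

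Elsewhere the SAP handles date-only records differently. In the 24-hour rescue endpoint, participants whose first rescue is dated up to the day after dosing and who have "missing first rescue medication time are excluded". The time-to-event section (5.2.3) refers to an imputed rescue start time without giving the imputation rule.

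**The concern.** A participant who follows the protocol cannot take rescue before the 2-hour entries. A date-only record from such a participant always describes rescue that came after the 15-, 30- and 60-minute and 2-hour assessments. The rule nevertheless overrides all of those that fall on the rescue date. Protocol Section 6.9.2 foresees this participant: relief at 2 hours, pain returning later, permitted rescue.

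The endpoints exposed are pain relief at 15 and 30 minutes (the first two steps of the key secondary sequence), return to normal function at 30 and 60 minutes, and the 2-hour endpoints, including both co-primaries. MBS freedom looks more exposed than pain freedom, because a participant can be free of the symptom at 2 hours, still have headache, and take rescue at once.

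No planned analysis would show the effect. The sensitivity analyses in SAP Section 5.3 cover only the co-primary endpoints, and they apply RM=F before imputing anything.

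**Working it through.** **1. What the rule does.** Both branches were coded and run on example records. Results with assessments present and entered at the target time:

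| Dose | Rescue | RM=F at, time recorded | RM=F at, date only |
|---|---|---|---|
| 09:00 | 11:30 same day (+2.5 h) | 3 h onward | all 12 time points |
| 09:00 | 14:00 same day (+5 h) | 6, 8, 24, 48 h | all 12 time points |
| 09:00 | 19:00 same day (+10 h) | 24, 48 h | all 12 time points |
| 20:00 | 01:00 next day (+5 h) | 6, 8, 24, 48 h | 4 h onward |
| 22:45 | 01:15 next day (+2.5 h) | 3 h onward | 90 min onward |

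The effect is tied to the calendar date: assessments before midnight on the previous date are untouched. The missing-assessment branch gives the same result for the three 09:00 rows. It does not alter the single-time-point main analyses, because a missing assessment is already a failure there.

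**2. How often a date-only record could truly precede the 15-minute entry.** Assume rescue time is uniform over what remains of the dosing date, ignoring the 2-hour bar.

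- Dose 10:00: 840 minutes remain, 15/840 = 1.8%.
- Dose 22:00: 120 minutes remain, 15/120 = 12.5%.
- Dose 22:30: 90 minutes remain. For the 60-minute entry, 60/90 = 67%.

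After a dose later than 22:00, a postdose rescue dated that day must fall within the first 2 hours. The rule can then be right.

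**3. Shift in the treatment difference.** The documents give none of these inputs. Assumed: same-day rescue 20% on zavegepant and 30% on placebo; 5% of rescue times missing (range 2-20%); 10-35% of rescuers were responders at the time point.

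Responses lost per arm = rescue share x missing-time share x responder share. Shift (zavegepant minus placebo) = placebo loss - zavegepant loss.

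| Responder share, zavegepant / placebo | Loss, zavegepant | Loss, placebo | Shift (points) |
|---|---|---|---|
| 10% / 10% | 0.10% | 0.15% | +0.05 |
| 35% / 35% | 0.35% | 0.525% | +0.175 |
| 35% / 10% | 0.35% | 0.15% | -0.20 |
| 23.2% / 15.1% (planned pain freedom) | 0.232% | 0.227% | about 0 |
| 40.5% / 32.1% (planned MBS freedom) | 0.405% | 0.482% | +0.08 |

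The last two rows borrow the 2-hour rates in Protocol Section 9.5 as responder shares, which is a further assumption. The sign changes where 0.20 x zavegepant share = 0.30 x placebo share, a ratio of 1.5. The range -0.20 to +0.18 holds if zavegepant rescuers were responders at least as often as placebo rescuers. The reverse corner (10% / 35%) gives 0.525 - 0.10 = +0.43. With 20% of times missing, every figure is multiplied by 4.

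In participants, the first two rows are 630 x 0.10% to 0.35% = 0.6 to 2.2 on zavegepant and 630 x 0.15% to 0.525% = 0.9 to 3.3 on placebo.

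**4. Power at 2 hours.** Protocol Section 9.5 gives 95.7%, 87.5% and about 84% jointly, at 630 per group. A two-proportion normal approximation at 2-sided 0.05 gives 95.7% and 87.5% with unpooled variance (product 83.7%), and 95.6% and 87.4% with pooled variance (product 83.5%). The plan's figures are reproduced. If the rule removes the same fraction of responders in both arms, joint power (pooled) goes from 83.5% to 82.8% at 1%, 82.1% at 2% and 79.9% at 5%. With 5% of times missing, and responders rescuing as often as everyone else, the fraction is 0.05 x 0.20 = 1.0% to 0.05 x 0.30 = 1.5%.

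**The case against.** The strongest reply is that the trigger is rare. The protocol requires the rescue time, and the Schedule of Activities has the rescue diary reviewed at the EOT Visit before data entry, so sites can resolve gaps. No missing-time rate appears in the documents, and every size above rests on assumed rates. The rule is also prespecified, identical in both arms, and in line with the plan's habit of counting the unknown as failure. All of this stands, and it limits how much the point matters. It does not make the rule match the estimand.

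Three stronger readings are tempting, and the documents do not support them.

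- *The rule favours zavegepant.* A reader might infer this from heavier rescue on placebo. It follows only if responder shares among rescuers are similar in the two arms; a higher share on zavegepant can cancel or reverse it. With no true early effect and response independent of later rescue, assumed rescue of 30% against 40-50% would raise the chance of a false result favouring zavegepant from 2.5% to at most 3.2% at 5% missing times. The extreme of 6.2% needs 20% missing and 30% against 50% rescue. The independence assumption probably overstates these figures, because early responders are likely to rescue less.
- *The rule is nearly always wrong at early time points.* This is true of a morning dose. It fails for late-evening doses, as step 2 shows.
- *The rescue-use endpoint contradicts the rule.* Rescue is the outcome there, so different handling of a missing time is not in itself a contradiction. The imputed time in Section 5.2.3 still needs its rule stated.

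**Conclusion.** The point holds as a low-priority correction. By its own wording, Appendix 2.1.2 turns genuine early responses into failures when a permitted later rescue on the same date lacks a time. That departs from the algorithm's aim and the estimands, and the protocol's 2-hour bar makes the presumption of early rescue implausible for most dose times.

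The size is probably a few tenths of a percentage point or less: about -0.2 to +0.2 at 5% missing times with 20% against 30% same-day rescue, under the responder-share conditions in step 3. The planned co-primary differences are 23.2 - 15.1 = 8.1 and 40.5 - 32.1 = 8.4 points. The direction is not determined. The number of date-only records is the quantity that matters, and it can be known only from the data.

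**What to change.** In Appendix 2.1.2, add one condition for time points before 2 hours when the rescue time is missing:

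- Rescue date equals the assessment date, and dose time plus 2 hours falls on that same date: do not apply RM=F.
- Rescue date equals the assessment date, but dose time plus 2 hours falls on a later date: keep RM=F, because the rescue must then lie within the first 2 hours.
- Rescue date before the assessment date: keep RM=F, because the dates settle the order.

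Leave the main rule unchanged at 2 hours and later. Repeat the two co-primary analyses with date-only same-day records not counted as rescue by 2 hours, as a sensitivity analysis. Report the number of date-only rescue records per arm. State the imputation rule that Section 5.2.3 relies on.

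The cost is SAP wording, one derivation condition and one extra run per co-primary endpoint. The downside is that a rare prohibited early rescue with no recorded time would be credited as a response at the early time points.

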### Appendix 3. AE Terms

#### Appendix 3.1. Potential Drug Abuse AEs

**Table 3. Potential Drug Abuse AE PTs from Clinical Review**

PTs
Abnormal sleep-related event
Abulia
Activation syndrome
Acute psychosis
Advanced sleep phase
Adverse drug reaction
Adverse reaction
Affect lability
Affective ambivalence
Affective disorder
Aggression
Agitated depression
Agitation
Alcohol abuse
Alcohol interaction
Alcohol problem
Alcohol use disorder
Alcohol withdrawal syndrome
Alcoholic hangover
Alcoholic psychosis
Alcoholism
Alexithymia
Alice in wonderland syndrome
Altered state of consciousness
Amnesia
Anaesthesia
Anger
Anhedonia
Antisocial behaviour
Apathy
Asocial behaviour
Asthenia
Auditory perseveration
Aura
Autoscopy
Aversion
Behavioural addiction
Binge drinking
Blunted affect
Borderline mental impairment
Boredom

**Table 3. Potential Drug Abuse AE PTs from Clinical Review**

PTs
Bradyphrenia
Brief psychotic disorder with marked stressors
Brief psychotic disorder without marked stressors
Brief psychotic disorder, with postpartum onset
Catatonia
Cholinergic syndrome
Circadian rhythm sleep disorder
Circumstantiality
Clang associations
Clinomania
Confabulation
Confusion postoperative
Confusional arousal
Confusional state
Consciousness fluctuating
Constricted affect
Cotard's syndrome
Crying
Decreased activity
Decreased interest
Deja vu
Delayed sleep phase
Delirium
Delusion
Delusion of grandeur
Delusion of reference
Delusion of replacement
Delusional disorder, erotomanic type
Delusional disorder, grandiose type
Delusional disorder, jealous type
Delusional disorder, mixed type
Delusional disorder, persecutory type
Delusional disorder, somatic type
Delusional disorder, unspecified type
Delusional perception
Dependence
Depersonalisation/derealisation disorder
Depressed level of consciousness
Depressed mood
Depression
Depression suicidal
Depressive delusion
Depressive symptom
Derailment
Derealisation

**Table 3. Potential Drug Abuse AE PTs from Clinical Review**

PTs
Diencephalic syndrome
Disinhibition
Disorganised speech
Disorientation
Dissociation
Dissociative amnesia
Dissociative disorder
Dissociative identity disorder
Disturbance in attention
Disturbance in social behaviour
Dopamine dysregulation syndrome
Dreamy state
Drug abuse
Drug dependence
Drug dependence, antepartum
Drug dependence, postpartum
Drug effect faster than expected
Drug interaction
Drug intolerance
Drug resistance
Drug tolerance
Drug tolerance decreased
Drug tolerance increased
Drug use disorder
Drug use disorder, antepartum
Drug use disorder, postpartum
Drug withdrawal headache
Drug withdrawal syndrome
Drug withdrawal syndrome neonatal
Dysphemia
Dysphoria
Dyssomnia
Egocentrism
Emotional disorder
Emotional distress
Emotional poverty
Erotomaniac delusion
Euphoric mood
Exploding head syndrome
Fatigue
Feeling abnormal
Feeling drunk
Feeling jittery
Feeling of despair
Feeling of relaxation

**Table 3. Potential Drug Abuse AE PTs from Clinical Review**

PTs
Feelings of worthlessness
Flashback
Flat affect
Flight of ideas
Formication
Frustration tolerance decreased
Gait deviation
Gait disturbance
Gait inability
Gambling disorder
Glassy eyes
Grandiosity
Hallucination
Hallucination, auditory
Hallucination, gustatory
Hallucination, olfactory
Hallucination, synaesthetic
Hallucination, tactile
Hallucination, visual
Hallucinations, mixed
Hangover
Homicidal ideation
Hyperarousal
Hyperkinesia
Hypersomnia
Hypervigilance
Hypnagogic hallucination
Hypnopompic hallucination
Hypoaesthesia
Hypokinesia
Hypomania
Hyporesponsive to stimuli
Hyposomnia
Hysterical psychosis
Ideas of reference
Idiosyncratic drug reaction
Illusion
Impulse-control disorder
Impulsive behaviour
Inadequate analgesia
Inappropriate affect
Incoherent
Inhibitory drug interaction
Initial insomnia
Insomnia

**Table 3. Potential Drug Abuse AE PTs from Clinical Review**

PTs
Intelligence increased
Intermittent explosive disorder
Intrusive thoughts
Irregular sleep phase
Irregular sleep wake rhythm disorder
Irritability
Jamais vu
Jealous delusion
Judgement impaired
Lack of spontaneous speech
Laziness
Lethargy
Libido disorder
Limited symptom panic attack
Listless
Logorrhoea
Loose associations
Loss of consciousness
Loss of control of legs
Loss of personal independence in daily activities
Magical thinking
Major depression
Malaise
Mania
Medication overuse headache
Memory impairment
Mental impairment
Middle insomnia
Mixed delusion
Moaning
Mood altered
Mood disorder due to a general medical condition
Mood swings
Morose
Narcolepsy
Neglect of personal appearance
Neologism
Neonatal complications of substance abuse
Neuroleptic-induced deficit syndrome
Nicotine dependence
Non-24-hour sleep-wake disorder
Panic attack
Panic disorder
Panic reaction
Paradoxical drug reaction

**Table 3. Potential Drug Abuse AE PTs from Clinical Review**

PTs
Paralogism
Paramnesia
Paranoia
Parasomnia
Paroxysmal perceptual alteration
Pathological doubt
Persecutory delusion
Perseveration
Personality change
Poor quality sleep
Postictal state
Potentiating drug interaction
Poverty of speech
Poverty of thought content
Preictal state
Premenstrual dysphoric disorder
Premenstrual syndrome
Pressure of speech
Pseudodementia
Pseudologia
Psychiatric decompensation
Psychogenic pseudosyncope
Psychomotor hyperactivity
Psychomotor retardation
Psychotic behaviour
Psychotic disorder
Psychotic symptom
Rapid eye movements sleep abnormal
Reactive psychosis
Rebound effect
Rebound psychosis
Schizoaffective disorder
Schizoaffective disorder bipolar type
Schizoaffective disorder depressive type
Schizophrenia
Schizophreniform disorder
Screaming
Seasonal affective disorder
Sedation
Sense of a foreshortened future
Sensory disturbance
Sensory loss
Sensory overload
Sensory processing disorder
Sexually inappropriate behaviour

**Table 3. Potential Drug Abuse AE PTs from Clinical Review**

PTs
Sleep deficit
Sleep disorder
Sleep inertia
Sleep sex
Sleep talking
Sleep terror
Sleep-related eating disorder
Slow response to stimuli
Sluggishness
Social avoidant behaviour
Somatic delusion
Somatic hallucination
Somnambulism
Somnolence
Sopor
Steroid withdrawal syndrome
Stupor
Substance abuse
Substance dependence
Substance use disorder
Substance-induced mood disorder
Substance-induced psychotic disorder
Sudden onset of sleep
Synaesthesia
Syncope
Tachyphrenia
Taciturnity
Tangentiality
Terminal insomnia
Therapeutic product effect decreased
Therapeutic product effect delayed
Therapeutic product effect incomplete
Therapeutic product effect increased
Therapeutic product effect prolonged
Therapeutic product effect variable
Therapeutic product effective for unapproved indication
Therapeutic response changed
Therapeutic response decreased
Therapeutic response delayed
Therapeutic response increased
Therapeutic response prolonged
Therapeutic response shortened
Therapeutic response unexpected
Thinking abnormal
Thought blocking

